1.1 STUDY OBJECTIVES AND ENDPOINTS

Table 1: Objectives and endpoints

Objectives	Endpoints
Primary	
To assess the long-term safety and tolerability of treatment with efgartigimod PH20 SC in participants with BP	
 • Incidence and severity of treatment-emergent AEs, SAEs, and AESIs • Rate of treatment discontinuation because of safety concerns
Secondary	
To assess the long-term efficacy and durability of response with efgartigimod PH20 SC treatment in participants with BP	
 • Proportions of participants achieving^a: 
 ○ CR while off OCS for ≥ 8 weeks ○ CR or PR while off OCS for ≥ 8 weeks ○ CR while on minimal OCS therapy for ≥ 8 weeks. (Minimal OCS therapy is defined as ≤ 0.10 mg/kg/day of prednisone [or an equivalent dose of another OCS]) ○ CR while off both OCS and efgartigimod PH20 SC for ≥ 8 weeks^b ○ CR or PR while off both OCS and efgartigimod PH20 SC for ≥ 8 weeks^b • Duration of sustained remission • Proportion of participants who relapse • Time to relapse • Incidence and severity of relapse • BPDAI activity scores, IGA-BP scores, and itch NRS over time • Rate of treatment failure

	Statistical Analysis Plan	
ARGX-113-2010	Final analysis	Final 1.0 of 29APR2025

Additional secondary	
To evaluate the impact of efgartigimod PH20 SC treatment in reducing long-term glucocorticoid-associated toxicity in participants with BP	
 GTI-related scores, including the GTI-AIS, GTI-CWS, and GTI-SL over time
To evaluate the impact of efgartigimod PH20 SC treatment on QoL in participants with BP	
 EQ-5D-5L, DLQI, and ABQOL scores over time
To evaluate the PD and immunogenicity of efgartigimod PH20 SC in participants with BP	
 Percent change from baseline over time for anti-BP180 and anti-BP230 antibody levels Incidence and prevalence of ADA against efgartigimod (serum levels)
Exploratory	
[REDACTED]	
 [REDACTED]

- ^a These endpoint criteria can only be met when participants are off rescue therapy.
- ^b The endpoint applies only to participants who have stopped receiving efgartigimod PH20 SC before protocol amendment 2 is effective.

1.2 STUDY DESIGN

This is a phase 3, open-label, prospective, global, multicenter, OLE study.

The total study duration is approximately 56 weeks comprising a treatment period of up to 48 weeks and a follow-up of approximately 8 weeks.

The study population is adult patients with BP who have completed ARGX-113-2009.

At rollover, all participants will receive efgartigimod PH20 SC after protocol amendment 2 (dated 26 April 2024) is effective. The treatment allocation of ARGX-113-2009 will remain blinded.

Participants who received placebo in ARGX-113-2009 and participants who have reinitiated efgartigimod PH20 SC treatment will receive [REDACTED] of efgartigimod PH20 SC [REDACTED] followed by once-weekly maintenance doses of efgartigimod PH20 SC 1000 mg.

Participants who received efgartigimod PH20 SC in ARGX-113-2009 will continue to receive once-weekly efgartigimod PH20 SC 1000 mg maintenance doses.

In earlier protocol versions (before protocol amendment 2 was effective), participants had to stop receiving efgartigimod PH20 SC after achieving CR or PR while off concurrent BP therapy for ≥ 8 weeks. For these participants, reinitiation of efgartigimod PH20 SC treatment will be at the investigator's discretion unless the participant relapses. Participants who relapse will initiate efgartigimod PH20 SC treatment.

Participants will visit the site at weeks 0 (baseline), 1, 2, 4, and 8. Thereafter, participants will attend site visits every 4 weeks. Participants not receiving efgartigimod PH20 SC will attend site visits every 8 weeks.

The schedule of assessments is in appendix 9.3.

	Statistical Analysis Plan	
ARGX-113-2010	Final analysis	Final 1.0 of 29APR2025

1.3 STATISTICAL HYPOTHESIS

No formal hypothesis testing will be conducted in this open-label study.

1.4 EXPECTED SAMPLE SIZE

The maximum number of participants in this study is the number of participants who complete the week 36/EoTP visit in ARGX-113-2009 and meet the eligibility criteria to roll over to this study.

1.5 RANDOMIZATION AND BLINDING

ARGX-113-2010 is open-label. The blinded allocation to efgartigimod PH20 SC or placebo from ARGX-113-2009 will be maintained until the database lock of ARGX-113-2009. Therefore, at rollover, participants receiving [REDACTED] on days 1 and 8 will receive 2 blinded injections with efgartigimod PH20 SC or 1 with efgartigimod PH20 SC and 1 with placebo. This will be handled via interactive response technology.

The blinding of immunogenicity data for ARGX-113-2010 will also be maintained until the database lock of ARGX-113-2009.

BP autoantibody data and albumin and total protein data collected from baseline through week 4 will remain blinded.

1.6 INTERIM ANALYSIS

No interim analyses are foreseen.

1.7 SOFTWARE

SAS version 9.4 or later (SAS Institute Inc., Cary, NC, USA) will be used for programming.

1.8 VALIDATION MODEL

SGS STAT Standard Operating Procedures (SOPs) and Work Instructions (Wis) as effective at the project start will be followed throughout the project, provided the applicable regulatory requirements are still met.

ADaM datasets, analysis tables, and listings will be validated according to model B (review by an independent person), except the following datasets: ADSL, ADAE and ADLB. These datasets will follow validation model C (review by an independent person and independent programming of the parameters indicated in this SAP). See SOP.STAT.020.

	Statistical Analysis Plan	
ARGX-113-2010	Final analysis	Final 1.0 of 29APR2025

2. GENERAL METHODOLOGY

2.1 ANALYSIS SETS

2.1.1 *Analysis sets*

The following participant analysis sets (PAS) will be used:

Rollover (ROL) analysis set: All participants who rolled over from ARGX-113-2009 and provided informed consent for participation in ARGX-113-2010

Safety (SAF) analysis set: All participants from the ROL analysis set who received at least one dose of IMP

Notes:

- Provided informed consent is defined as having a complete informed consent signature date in the database.
- Received at least one dose of IMP is defined as having an exposure date or any information confirming exposure present in the database.

2.1.2 *As planned versus as actual analysis*

Not applicable. All endpoints will be analyzed for the total group of participants, regardless of previous treatment in ARGX-113-2009 (placebo or efgartigimod PH20 SC).

2.2 PHASES, PERIODS AND TIME POINTS

2.2.1 *Analysis phases, periods and subperiods*

All assessments and events will be allocated to analysis phases, periods and subperiods as defined in below table.

Table 2: Analysis phase, period and subperiod definition

Phase	Period/Subperiod	Start	End
For participants who don't receive the first IMP administration at the ARGX-113-2010 baseline visit^a, the first phase will be the observation phase.			
For participants who receive the first IMP administration at the ARGX-113-2010 baseline visit^a, the first phase will be the treatment phase.			
Observation		Date of baseline visit in ARGX-113-2010, with 00:00 added as time part	
For participants with a subsequent treatment period:
 
First IMP administration date/time – 1 minute.
 
For other participants:
 
Date of week 48 or EDV visit^c, with 23:59 added as time part.
 
For participants who don't have a week 48 or EDV visit: date of last contact, with 23:59 added as time part.

	Statistical Analysis Plan	
ARGX-113-2010	Final analysis	Final 1.0 of 29APR2025

Phase	Period/Subperiod	Start	End
Treatment	Treatment period 1/ On IMP treatment	
For participants with first IMP administration at the baseline visit:
 
Date of baseline visit in ARGX-113-2010, with 00:00 added as time part.
 
For participants with a previous observation phase and who initiate treatment:
 
First IMP administration date/time
	
For participants with a subsequent Off IMP subperiod:
 
Last IMP administration date/time in treatment period 1.
 
For other participants:
 
Date of week 48 or EDV visit^c, with 23:59 added as time part.
 
For participants who don't have a week 48 or EDV visit: date of last contact, with 23:59 added as time part.

	Treatment period 1/ Off IMP treatment	Last IMP administration date/time in treatment period 1 + 1 minute	
For participants with a subsequent treatment period:
 
First IMP administration date/time in next treatment period – 1 minute.
 
For other participants:
 
Date of week 48 or EDV visit^c, with 23:59 added as time part.
 
For participants who don't have a week 48 or EDV visit: date of last contact, with 23:59 added as time part.

Treatment period 2 is applicable for participants who re-initiate IMP administration after a previous Off IMP subperiod^b.			
Treatment	Treatment period 2/ On IMP treatment	First IMP administration date/time in treatment period 2	
For participants with a subsequent Off IMP subperiod:
 
Last IMP administration date/time in treatment period 2.
 
For other participants:
 
Date of week 48 or EDV visit^c, with 23:59 added as time part.
 
For participants who don't have a week 48 or EDV visit: date of last contact, with 23:59 added as time part.

	Treatment period 2/ Off IMP treatment	Last IMP administration date/time in treatment period 2 + 1 minute	
Date of week 48 or EDV visit^c, with 23:59 added as time part.
 
For participants who don't have a week 48 or EDV visit: date of last contact, with 23:59 added as time part.

	Statistical Analysis Plan	
ARGX-113-2010	Final analysis	Final 1.0 of 29APR2025

Phase	Period/Subperiod	Start	End
Follow-up		End of previous phase + 1 minute	Date of last contact, with 23:59 added as time part.

- ^a First IMP administration is considered to occur on the ARGX-113-2010 baseline visit if the date of first IMP administration equals the scheduled baseline visit start date (SVSTDTC) or end date (SVENDTC), or if the first IMP administration occurs on an unscheduled baseline visit. In either case, the first phase starts with SVSTDTC of the first scheduled or unscheduled baseline visit.
- ^b A new treatment period is considered for participants with relapse after achieving CR or PR while being off concurrent BP therapy for ≥ 8 weeks before protocol amendment 2 was effective, or at the investigator's discretion after protocol amendment 2 was effective. For programming purposes, a new treatment period will be considered if a participant has a gap of at least 4 weeks (28 days) between two consecutive IMP administrations that cannot be attributed to missed visits or non-efficacy related reasons documented on the study drug administration eCRF form.
- ^c SVENDTC of the last scheduled or unscheduled week 48 or early discontinuation visit will be used.

Adverse events will be allocated to phases as described in section 5.1.2. Concomitant therapies and procedures will be allocated to phases and (sub)periods as described in section 3.3.2. All other assessments will be allocated to phases and (sub)periods based on the assessment date/time. In case of (partially) missing date/time fields disabling allocation of an assessment to phases or (sub)periods, information from the visit label, time point label and the protocol schedule of activities will be used to allocate to the correct phase.

For efficacy assessments without time part, an assessment on the day of switch from observation phase to treatment phase will be considered as part of the treatment phase. Likewise, an assessment on the day of switch from treatment period 1 to treatment period 2 will be considered as part of treatment period 2.

2.2.2 *Baseline and change from baseline*

Study baseline is defined as the first available and nonmissing value at the baseline visit (scheduled or unscheduled) in ARGX-113-2010. This value corresponds with the value at the EoTP visit in ARGX-113-2009 (and is copied over into the database of ARGX-113-2010 at SDTM level).

Change from baseline is defined as:

- Change from baseline at time point t = value at time point t – baseline value.

Percentage change from baseline at time point t is defined as follows:

- When baseline value is not zero: $100 * ((\text{value at time point } t - \text{baseline value}) / \text{baseline value})$
- When both baseline value and value at time point t are zero: 0
- When baseline value is zero and value at time point t is not zero: not calculated

For immunogenicity assessments, the study baseline selection will be performed by sample (not by parameter) in order to keep the ADA and NAb results of a sample together. Furthermore, values resulting in an unevaluable ADA status are given the lowest priority when the selection is made.

For evaluation of PD parameters, a treatment period-specific baseline (TPnB) will be defined:

	Statistical Analysis Plan	
ARGX-113-2010	Final analysis	Final 1.0 of 29APR2025

- For a treatment period, TPnB is the last available and non-missing value prior to the first IMP administration in the treatment period. Assessments on day 1 of a treatment period without time collection or with time information exactly equal to the time of first IMP administration and which are planned predose will be considered as predose.
- For the observation phase, TPnB corresponds with the study baseline.
- For the follow-up phase, TPnB corresponds with TPnB of the preceding phase/period.

2.2.3 *Relative day*

The relative day in the study is calculated as follows:

- ADY = assessment date – baseline visit date, if assessment date is before the baseline visit date
- ADY = assessment date – baseline visit date +1, if assessment date is on or after the baseline visit date

The relative day in a subperiod (refer to Section 2.2.1) is calculated as:

$$AWADY = \text{assessment date} - \text{subperiod start date} + 1$$

For the observation phase, AWADY corresponds with ADY. For the follow-up phase, AWADY will be calculated with reference to the follow-up phase start date.

2.2.4 *Analysis visits*

All assessments, including unscheduled assessments, will be allocated to analysis visit windows. Tables and listings will present the analysis visit as defined below, not the eCRF visits. Allocations of assessments will be performed using AWADY (see section 2.2.3) according to Table 3 below:

Table 3: Analysis visits

Phase/Period/ Subperiod	Analysis visit	Target AWADY	Lower limit AWADY	Upper limit AWADY
Observation phase	Baseline ^a	-	-	-
	Week 2 ^d	15	1	22
	Week 4	29	23	43
	Week 8	57	44	85
	Week x ^b	T=7*x+1	integer[(T + Tp)/2]+1 ^c	integer[(T + Tn)/2] ^c
Treatment phase/ Treatment period 1/ On IMP treatment	Baseline ^a / TP1B	-/ Relative day of first IMP admini- stration	-/-Inf	-/ Relative day of first IMP administration
	Week 2 ^d	15	1/ Relative day of first IMP administration	22
	Week 4	29	23	43
	Week 8	57	44	71
	Week x ^b	T=7*x+1	integer[(T + Tp)/2]+1 ^c	integer[(T + Tn)/2] ^c

	Statistical Analysis Plan	
ARGX-113-2010	Final analysis	Final 1.0 of 29APR2025

Phase/Period/ Subperiod	Analysis visit	Target AWADY	Lower limit AWADY	Upper limit AWADY
Treatment phase/ Treatment period 1/ Off IMP treatment	Week 8	57	1	85
	Week x ^b	$T=7*x+1$	$\text{integer}[(T + T_p)/2]+1^c$	$\text{integer}[(T + T_n)/2]^c$
Treatment phase/ Treatment period 2/ On IMP treatment	TP2B	1	-Inf	1
	Week 2 ^d	15	1	22
	Week 4	29	23	43
	Week 8	57	44	71
	Week x ^b	$T=7*x+1$	$\text{integer}[(T + T_p)/2]+1^c$	$\text{integer}[(T + T_n)/2]^c$
Treatment phase/ Treatment period 2/ Off IMP treatment	Week 8	57	1	85
	Week x ^b	$T=7*x+1$	$\text{integer}[(T + T_p)/2]+1^c$	$\text{integer}[(T + T_n)/2]^c$
Follow-up phase	FU Week 4	29	1	43
	FU Week 8	57	44	End day of FU phase

^a The baseline analysis visit will be assigned to the first phase that is applicable for a participant, either the observation phase or the treatment phase. The baseline visit is defined in section 2.2.2 and does not require definition of analysis visit limits.

^b x increases in steps of 4 weeks (On IMP subperiods) or 8 weeks (observation phase or Off IMP subperiods) up till the point where the upper limit of the analysis visit window exceeds the end day of the phase/subperiod. In this case the upper limit will be cut at the end day of the phase/subperiod. The maximum value of x is week 48.

^c T = target day of current analysis visit, T_n = target day of next window, T_p = target day of previous window.

^d An assessment on AWADY = 1 that is not selected as Baseline/TPnB will be assigned to Week 2.

Baseline and TPnB are defined in section 2.2.2.

Per parameter and analysis visit, the nonmissing value closest to the target AWADY will be used in analysis tables, other values will only be listed. If more than one nonmissing value is located at the same distance from the target, then the one latest in time will be selected for analysis. The value latest in time will be identified using, in order of preference, the assessment date(time), the visit label, the database group identifier or sequence number.

For immunogenicity assessments, the selection will be performed by sample (not by parameter) and analysis visit in order to keep the ADA and NAb results of a sample together. Furthermore, values resulting in an unevaluable ADA status are given the lowest priority when the selection is made.

Missing assessment dates will be imputed with the corresponding visit date. If there is no corresponding visit date available, the assessment will not be allocated to an analysis visit.

2.2.5 *Worst-case*

A worst-case analysis visit will be created for parameters with defined abnormalities and/or toxicity grades (e.g., labs, vital signs, ECGs). For abnormalities, the worst-case is derived per parameter and if both the lowest and highest values are considered abnormal, a participant can have two worst-case analysis visits for the same

	Statistical Analysis Plan	
ARGX-113-2010	Final analysis	Final 1.0 of 29APR2025

parameter. For toxicity grades, the worst-case is the value associated with the highest toxicity grade and is derived per parameter and toxicity direction (hypo/hyper).

All nonmissing postbaseline values on or after the first administration of IMP in ARGX-113-2010 and up to and including 60 days after the last IMP administration before the assessment will be considered when deriving the worst-case analysis visit. This may include unscheduled assessments, assessments not selected for the analysis visit and assessments during the follow-up phase.

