ARGX-113-2010	Final analysis	Final 1.0 of 29APR2025

Else, the participant will be considered a CR/PROff non-responder. Participants who already have the disease status CR or PR at day 1 of the treatment period or who are off OCS therapy at day 1 of the treatment period or who receive rescue therapy at day 1 of the treatment period, will be considered non-evaluable for this endpoint and will be excluded from this analysis for the corresponding treatment period.

- 3) Participants achieving CR while on minimal OCS therapy for ≥ 8 weeks (CRmin). A participant will be considered a CRmin responder if the following criteria are met simultaneously for ≥ 8 weeks (56 days):
- The participant's reported disease status is CR
 - The participant receives ≤ 0.10 mg/kg/day of prednisone (or an equivalent dose of another OCS)
 - The participant does not receive any rescue therapy (as indicated by the investigator on the eCRF). OCS used as rescue therapy will not be considered as rescue therapy if the above criterium of minimal OCS therapy is still met.

Else, the participant will be considered a CRmin non-responder. Participants who already have the disease status CR at day 1 of the treatment period or who are on minimal (≤ 0.10 mg/kg/day) OCS therapy at day 1 of the treatment period or who receive rescue therapy at day 1 of the treatment period, will be considered non-evaluable for this endpoint and will be excluded from this analysis for the corresponding treatment period.

- 4) Participants with treatment failure.

The following endpoints will be derived **for each treatment period separately and additionally for the observation phase:**

- 5) Participants achieving CR while off both OCS and efgartigimod PH20 SC for ≥ 8 weeks (CROff without IMP). A participant will be considered a responder for CROff without IMP if the following criteria are met simultaneously for ≥ 8 weeks (56 days):
- The participant's reported disease status is CR
 - The participant is off OCS therapy
 - The participant is off IMP
 - The participant does not receive any rescue therapy (as indicated by the investigator on the eCRF)

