Else, the participant will be considered a non-responder for CROff without IMP. Participants who enter the ARGX-113-2010 study under protocol version 3 (26 April 2024) or 4 (02 May 2024) will be considered non-evaluable for this endpoint. Furthermore, participants who were randomized to the placebo arm in the ARGX-113-2009 study and who enter the ARGX-113-2010 study in the observation phase, will be considered non-evaluable for this endpoint in the observation phase.

- 6) Participants achieving CR or PR while off both OCS and efgartigimod PH20 SC for ≥ 8 weeks (CR/PROff without IMP). A participant will be considered a

	Statistical Analysis Plan	
ARGX-113-2010	Final analysis	Final 1.0 of 29APR2025

responder for CR/PROff without IMP if the following criteria are met simultaneously for ≥ 8 weeks (56 days):

- The participant's reported disease status is CR or PR (continuously or alternately)
- The participant is off OCS therapy
- The participant is off IMP
- The participant does not receive any rescue therapy (as indicated by the investigator on the eCRF)

Else, the participant will be considered a non-responder for CR/PROff without IMP. A participant will be considered non-evaluable for this endpoint using the same rules as for CROff without IMP.

- 7) Duration of sustained remission will be calculated for participants achieving CR while off both OCS and efgartigimod PH20 SC for ≥ 8 weeks (i.e., responders for CROff without IMP) within a treatment period.
 - Start date of sustained remission is 1 week (7 days) after the last IMP administration in the treatment period
 - End date of sustained remission is:
 - the start date of first relapse after achieving CROff without IMP
 - the start date of a (next) treatment period
 - the start date of OCS therapy after achieving CROff without IMP
 - the start date of a rescue therapy after achieving CROff without IMP
 whichever comes first. If none of the above occurs, the participant will be censored at the end date of the study (end date of last phase).
 - Duration of sustained remission (in days) = end date - start date + 1
- 8) Relapse will be evaluated for participants having or achieving CDA, CR or PR during the treatment period (or observation phase). The evaluation period for relapse is till the end of the treatment period (or observation phase) in case a (next) treatment period starts, or else till the end of the study. Only the first relapse in a treatment period (or observation phase) will be considered.

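### SAP items 5 and 6 state no lag for being off IMP, but item 7 starts sustained remission for the item 5 responders 7 days after the last dose, so a 56-day responder can be reported with a 51-day remission

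*SAP*

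**What the plan says.** - **SAP 2.2.1, Table 2.** The Off IMP subperiod of treatment period 1 starts at "Last IMP administration date/time in treatment period 1 + 1 minute"; treatment period 2 follows the same rule. The table is introduced as an allocation rule: "All assessments and events will be allocated to analysis phases, periods and subperiods as defined in below table".
- **SAP 4.1.2, items 5 and 6.** A responder must meet all criteria together for at least 8 weeks, given as 56 days. One criterion reads only "The participant is off IMP". There is no lag and no cross-reference.
- **SAP 4.1.2, item 7.** The duration is calculated for the "responders for CROff without IMP". "Start date of sustained remission is 1 week (7 days) after the last IMP administration in the treatment period". The end date is the earliest of several events, among them "the start date of first relapse after achieving CROff without IMP"; otherwise the participant is censored at the end of the last phase. The formula is "Duration of sustained remission (in days) = end date - start date + 1".
- **SAP 1.2.** Maintenance dosing is once weekly.
- **Protocol, Definitions of Terms.** For participants already in the study when amendment 2 took effect, sustained remission requires at least 8 weeks off both concurrent BP therapy and efgartigimod.

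**The concern.** Item 7 is built directly on item 5: the same participants and the same last dose. The two items should therefore agree on when the participant went off drug. As written they need not. Item 5, read with the only off-IMP boundary in the SAP, counts from immediately after the last dose, whereas item 7 counts from a week later.

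At stake is the coherence of the off-drug durability endpoints. Table 14.2.1.6 (Kaplan-Meier estimates of the duration of sustained remission) could show durations below the 8-week threshold that admitted the participant to that table. Two programmers could also classify the same borderline participant differently in Tables 14.2.1.4 and 14.2.1.5, each with a defensible reading of the text.

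**Working it through.** **Inputs.** Off-IMP boundary: last dose + 1 minute (SAP Table 2). Required run: 56 days (items 5 and 6). Start of remission: last dose + 7 days (item 7). Duration: end − start + 1 (item 7). Call the date of the last dose day 0.

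**Step 1, the plan's own figure.** 8 × 7 = 56 days, as stated.

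**Step 2, item 5 read with Table 2.** The first full off-drug day is day 1. The last of 56 qualifying days is 1 + 56 − 1 = day 56, so the earliest event that can end the remission of a qualified responder falls on day 57.

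**Step 3, item 7 for the same participant.** An event on day k gives k − 7 + 1 days.

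| Relapse on day | Item 5 response | Item 7 duration (days) |
|---|---|---|
| 57 | yes | 57 − 7 + 1 = 51 |
| 61 | yes | 61 − 7 + 1 = 55 |
| 62 | yes | 62 − 7 + 1 = 56 |

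**Step 4, other ways of counting.**
- Censored on day 56: 56 − 7 + 1 = 50.
- Dose date counted as the first off-drug day, so the run ends on day 55: event on day 56 gives 56 − 7 + 1 = 50; censored on day 55 gives 55 − 7 + 1 = 49.

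So 51 days is the shortest event duration when day 1 is the first off-drug day; it is not an absolute minimum.

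**Step 5, days in dispute.** Item 7 starts on day 7 and counts that day. Days 1 to 6 count under step 2 but not under item 7: 6 / 56 = 10.7%.

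**Step 6, one date for all three items.**
- First off-IMP day = day 7: the run ends on 7 + 55 = day 62. Event on day 63 gives 63 − 7 + 1 = 57; censored on day 62 gives 62 − 7 + 1 = 56.
- First off-IMP day = day 1: event on day 57 gives 57 − 1 + 1 = 57; censored on day 56 gives 56 − 1 + 1 = 56.

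Either choice removes every duration below 56 days.

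**Step 7, how many participants (illustrative).** The documents give no relapse rate after stopping. Assume an exponential time to relapse from the last dose. Response status depends on the choice between day 1 and day 7 for relapses on days 57 to 62.

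| Assumed median | Share of stoppers, S(56) − S(62) | Share of apparent responders, 1 − exp(−ln2 × 6 / median) |
|---|---|---|
| 56 days | 3.6% | 7.2% |
| 168 days | 1.9% | 2.4% |
| 336 days | 1.1% | 1.2% |

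**The case against.** **The link to Table 2 is not in the text.** Table 2 exists to allocate assessments and events, and items 5 and 6 do not cite it. Since item 7 rests on item 5, its 7-day start could be read as showing the intended convention for all three items. On that reading no duration falls below 56 days. This stands as a limit on the claim: the SAP shows an undefined term with two candidate dates, not a settled error. It does not remove the need to define the term. The nearest other rule, the day-level OCS rule in SAP 3.4.2, also has no carry-over; applied by analogy it would make the day after the last dose the first off-drug day.

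**Table 2 agrees with the protocol's usage.** The protocol synopsis describes an 8-week treatment-free period after the week 48 visit, which is also the last possible dosing time point, and section 7.1.1 times safety follow-up from the final administration. Item 7's lag is then the outlier, and it shortens the reported duration. This stands too. It means that the choice between the two dates is open, but not that both can be used.

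**The consequences are small.** SAP 1.3 foresees no hypothesis test. Participants entering under protocol version 3 or 4 are non-evaluable for items 5 and 6. No dose in this study precedes the observation phase, so it is unaffected. All of this stands.

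**Conclusion.** The inconsistency is real and worth correcting. Read literally, a relapse 57 to 61 days after the last dose yields a responder for at least 56 days whose sustained remission is 51 to 55 days. This rests on taking Table 2 as the source of the off-IMP date and day 1 as the first off-drug day. The size is modest: 6 of 56 days differ, in descriptive secondary endpoints. Under the assumed medians, about 1% to 4% of stoppers, or 1% to 7% of apparent responders, fall in the band where the choice of date decides response.

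Three stronger readings are tempting but not supported:

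- **That the off-drug response is met under drug cover, so the proportions are too favourable.** Neither document says how long a dose counts as active for this endpoint. The weekly interval is a dosing schedule, and item 7's lag alone does not show that items 5 and 6 are biased.
- **That a full 7 of the 56 days are affected.** That holds only if the dose date itself counts as off drug. Counted from day 1, it is 6.
- **That Table 2 is wrong and should be moved by a week.** The early discontinuation visit is due within 7 days of the final dose (protocol 7.1.1) and can end the Off IMP subperiod, so a later start could fall after its end. The relative day in a subperiod counts from the subperiod start (SAP 2.2.3), so every Off IMP visit window in Table 3 would also shift. Assigning a therapy begun in that week to Off IMP in the concomitant-therapy tables is a matter of labelling and changes no endpoint.

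**What to change.** Leave Table 2 unchanged. In SAP 4.1.2, define the first off-IMP day of a treatment period once, and refer to that definition in items 5, 6 and 7. One workable choice is the date of last IMP administration + 7 days, counted inclusively as item 7 already does. The 56 days then run from day 7 to day 62, and the shortest duration is 57 days with an event or 56 days if censored. Using the day after the last dose in all three items would be equally coherent, but would change item 7 instead.

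The cost is a sentence of SAP text and one date derivation. With the +7-day choice, a few borderline responders become non-responders: those who relapse on or before day 62, or whose observation ends before day 62.

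One consequence should be settled at the same time. The SAP does not say whether follow-up days count towards items 5 and 6. If they do, an evaluable participant dosed at week 48 has a final visit at EoTP + 8 weeks ± 3 days, which is day 53 to 59 if the last dose is given at the EoTP visit. That participant could not reach day 62; an on-schedule visit on day 56 gives 56 − 7 + 1 = 50 days. The authors should choose the date with that in view and state it.
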